Should a patient need to be discontinued from the study before week 10, he/she will be asked to return to NYSPI or to complete a telehealth evaluation and an assessment with their local physician (if participating remotely) to complete the major week 8/10 assessments so that his/her progress can continued to be evaluated by the study clinician. Since we do not know the optimal duration of disulfiram (ie, shorter courses may be effective) and because improvement may occur during the weeks after discontinuation, we will ask patients to return at week 10 (or to complete telehealth and local evaluations) but also to complete self-reports assessments and telephone follow-up at home at weeks 2, 6, 8, and 14.

Should a patient who drops from treatment early plan to start a new treatment that might impact clinical ratings, we will ask the patient to complete the full set of week 10 assessments early so that these can be used in the final data analysis; that patient will then be discontinued from both the treatment and assessment phase of the study. The patient will also be asked to return all study medication which we will then return to the NYSPI pharmacy.

During COVID-19 pandemic: I attest to follow the COVID-19 Safety Guidelines for Columbia Psychiatry and NYSPI Re-Entry outlined in the NYSPI Director's June 1st memo, which include but are not limited to:

• Infection Control/PPE – Guidelines

• Research participants will only come on-site if absolutely necessary for study procedures.

• No volunteers/externs on-site during Stage 1.

• Clinical research teams will screen their participants for COVID symptoms (night before and day of onsite visit, documenting this in the chart), and escort them in and out of the building.

• COVID/COVID-like symptoms in participants will be reported to the IRB via PRISM as an SAE.

You can upload charts or diagrams if any

Criteria for Early Discontinuation

Criteria for Early Discontinuation

Patients will be monitored for global clinical change (CGI Change - clinician rating) and for side-effects of the medications (Saftee) during the clinic visits or telehealth visits and weekly phone check-ups.

• A patient will be discontinued from treatment early if he/she shows signs of liver toxicity on laboratory tests; an abnormal finding (e.g., Moderate or Severe ALT elevation > 2x ULN or AlkPhos > 1.5x ULN or Bili > 1.5x ULN) will lead to a discontinuation of the treatment, repeat of the lab test with close monitoring of the patient, and a referral for the patient to see their internist for further liver monitoring. If patients experience any mild ALT elevation or Alk Phos elevation (e.g., ALT >ULN but <2x ULN or ALK Phos >ULN <1.5x ULN), then the study clinician will keep their disulfiram dose the same and repeat testing in 2 weeks as long as their TB remains <1.5 ULN. Patients will be advised to immediately notify their study clinician of any early symptoms of hepatitis, such as fatigue, weakness, malaise, anorexia, nausea, vomiting, jaundice or dark urine; this will lead to a medical evaluation to rule out liver involvement.

• Patients will also be discontinued from the treatment component of the study early if they experience any new onset adverse neurological reactions thought to be due to the study treatment and which persists for at least 1 week (e.g., polyneuritis, peripheral neuropathy).

Clinically, early discontinuation from treatment will occur if:

a. a patient's self-report on the CGI Global Change scale indicates a score of "very much worse" for 2 consecutive weeks or "much worse" for 4 consecutive weeks.

b. a patient's score on the BDI item 9 suicide item is 2 or higher for 2 consecutive assessments. A BDI item 9 score of 2 or 3 will lead to an evaluation by a psychiatrist and closer monitoring which will include a reassessment one week later. If the worsening suicidal ideation continues, the patient will be withdrawn from the study and appropriate clinical care will be arranged.

Blood and other Biological Samples

Please create or insert a table describing the proposed collection of blood or other biological specimens

IN-PERSON PARTICIPANT SPECIMEN COLLECTION:

The following will be drawn or collected for in-person participants:

Intake

- CBC, Chemistry Screen, TFT (Tests performed at NKI)
- 1. CBC- 1 4cc EDTA
- 2. TFTs and Chemistry Screen- 2, 8cc Red Top
- 3. Tox Screen and Pregnancy Test- 50 cc Urine

Lyme and Babesia test (Tests performed at MDL) 1. 2, 8.5cc Serum Tube

Stool collection kit is given to patient at intake visit. Patient is to collect stool sample at home and send to [name] lab at Northeastern- kits prior to the Baseline visit.

Baseline/Wk0

Lyme Proteome Test (Test performed at George Mason University) 1. 80cc Urine Sample

Storage for Biorepository-

- 1. 2, 8 cc Red top Serum Tube- stored in .25cc aliquots
- 2. 1, 8cc EDTA Plasma-tube stored in .5cc aliquots
- 3. 1, 4cc EDTA Whole Blood stored in .5cc aliquots

CBC, Chemistry Screen, LFT (Tests performed at NKI)1. CBC- 1 4cc EDTA2. TFTs and Chemistry Screen- 2, 8cc Red Top

Weeks 1, 2, 4, 6, 8 CBC and Chem screen (including LFTs). Urine Tox Screen at Wks 2 and Wk 6

Week 4 & 8

Storage for Biorepository-

- 1. 1, Serum from one 8cc Red Top Tube
- 2. 1, Plasma from one 6cc EDTA Plasma Tube
- 3. 50cc Urine Sample

Stool sample (collected at home and sent to [name] lab at Northeastern)

Week 10

- CBC and Chem screen (including LFTs)
- 1. CBC-1 4cc EDTA
- 2. TFTs and Chemistry Screen- 2 8cc Red Top

Lyme Proteome Test (Test performed at George Mason University) 1. 80cc Urine Sample

Storage for Biorepository-

- 1. 2, 8 cc Red Top Serum Tube- stored in .25cc aliquots
- 2. 1, 8cc EDTA Plasma-tube stored in .5cc aliquots
- 3. 1, 4cc EDTA Whole Blood stored in .5cc aliquots

Stool sample (collected at home and sent to [name] lab at Northeastern)

REMOTE PARTICIPANT SPECIMEN COLLECTION:

The following will be drawn or collected for remote participants:

Intake

CBC, Chemistry Screen, TFT (Tests performed at Quest Diagnostics)

- 1. CBC-1 4cc EDTA
- 2. TFTs and Chemistry Screen- 2, 8cc Red Top

3. Tox Screen and Pregnancy Test- 50 cc Urine

Lyme and Babesia test (Tests performed at MDL) 1. 2, 8.5cc Serum Tube

Stool collection kit is mailed to patient after intake telehealth visit. Patient is to collect stool sample at home and send to [name] lab at Northeastern prior to the Baseline visit.

Baseline/Wk0

Lyme Proteome Test (Test performed at George Mason University) 1. 80cc Urine Sample (Participants will be mailed a urine collection kit. Urine sample is to be collected at home and sent to George Mason University collaborators)

Weeks 2, 4, & 6

CBC and Chem screen (including LFTs). Urine Tox Screen at Wk 6 only (Tests performed at Quest Diagnostics)

Week 4 & 8 Stool sample (collected at home and sent to [name] lab at Northeastern)

Week 10

CBC and Chem screen (including LFTs) - (Tests performed at Quest Diagnostics)

1. CBC-1 4cc EDTA

2. TFTs and Chemistry Screen- 2 8cc Red Top

Lyme Proteome Test (Test performed at George Mason University) 1. 80cc Urine Sample (Urine sample is to be collected at home and sent to George Mason University collaborators)

Stool sample (collected at home and sent to [name] lab at Northeastern)

HYBRID PARTICIPANT SPECIMEN COLLECTION:

The following will be drawn or collected for remote participants:

Intake

CBC, Chemistry Screen, TFT (Tests performed at Quest Diagnostics)

1. CBC-1 4cc EDTA

- 2. TFTs and Chemistry Screen- 2, 8cc Red Top
- 3. Tox Screen and Pregnancy Test- 50 cc Urine

Lyme and Babesia test (Tests performed at MDL)

1. 2, 8.5cc Serum Tube

Stool collection kit is mailed to patient after intake telehealth visit. Patient is to collect stool sample at home and send to [name] lab at Northeastern prior to the Baseline visit.

Baseline/Wk0

Storage for Biorepository- Collected at NYSPI

- 1. 2, 8 cc Red top Serum Tube- stored in .25cc aliquots
- 2. 1, 8cc EDTA Plasma-tube stored in .5cc aliquots
- 3. 1, 4cc EDTA Whole Blood stored in .5cc aliquots

Lyme Proteome Test (test performed at George Mason University) 1. 80cc Urine Sample - collected at NYSPI

Weeks 2, 4, & 6

CBC and Chem screen (including LFTs). Urine Tox Screen at Wk 6 only (Tests performed at Quest Diagnostics). Stool sample at Wk 4 only (collected at home and sent to [name] lab at Northeastern)

Week 8

Stool sample (collected at home and sent to [name] lab at Northeastern)

Week 10

CBC and Chem screen (including LFTs) - (Tests performed at Quest Diagnostics) 1. CBC- 1 4cc EDTA 2. TFTs and Chemistry Screen- 2 8cc Red Top

Storage for Biorepository-

- 1. 2, 8 cc Red Top Serum Tube- stored in .25cc aliquots
- 2. 1, 8cc EDTA Plasma-tube stored in .5cc aliquots
- 3. 1, 4cc EDTA Whole Blood stored in .5cc aliquots
- Lyme Proteome Test (Test performed at George Mason University)

1. 80cc Urine Sample - collected at NYSPI

Stool sample (collected at home and sent to [name] lab at Northeastern)

Assessment Instruments

Create a table or give a brief description of the instruments that will be used for assessment Participants will complete the following questionnaires. Detailed information on what intervals these questionnaires will be completed is attached below.

- Overall Multi-Domain Assessment:
- 1. Promis 29
- 2. Patient-rated Clinical Global Improvement

Somatic Symptoms

- 1. General System Questionnaire- 30 items
- 2. VAS for "Fatigue"
- 3. Fatigue Severity Scale

Psychopathology:

- 1. Depression: Beck Depression Inventory II; (and PROMIS module)
- 2 Anxiety: STAI (and PROMIS module)
- 3. MINI-Neuropsychiatric Assessment

Cognition:

- 1. Keilp Cognitive Battery or Abbreviated Cognitive Battery for remote and hybrid participants
- 2. NeuroQoL-Short Form v2.0 Cognition
- 3. VAS- for "Brain Fog"
- 4. Mini Mental Status (for participants 60 and older)

Functional Status

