3. We will examine the side effect profile and drop-out rate associated with different treatment schedules of disulfiram.

4. We will examine whether there are other self-report measures that are more sensitive in documenting change over time than the FSS and the Q-LES-Q. These other measures, for example, include the PROMIS 29 v2.0 profile questionnaire, the SF-36, and the General Symptom Questionnaire (GSQ-30).

5. We will examine whether tests of sensory function, autonomic function, and cognitive function change with treatment.

6. We will examine whether the urine antigen marker of Borrelia burgdorferi (as assessed by the Ceres Nanoscience Urine Nanotrap assay) is present at baseline and not present after treatment.

7. We will collect biological samples for future precision medicine studies to be stored in our repository.

8. We will collect fecal samples to be probed by investigators interested in studying microbiome changes in response to disulfiram.

9. We will also monitor patients' activity via the data generated by Fitbit- The rationale for the Fitbit is that our primary outcome is fatigue. People who are less fatigued may be engaging in more activity, such as doing more steps during the day. Moreover, activity monitoring using a device such as a Fitbit is being increasingly used in research studies as a measure of the change in response to treatment.

REMOTE PARTICIPATION CONSIDERATIONS:

Due to the challenges imposed with remote data collection, we will not address research aims addressing sensory and autonomic function (aim 5), or collection of biological specimens for our repository (aim 7). Capacity to address these aims is dependent on final numbers of in-person vs. remote study participation. In light of the current COVID-19 pandemic, no in-person procedures will be conducted at NYSPI and we are unable to estimate future in-person enrollments at this time.

Description of Subject Population

Sample #1

Specify subject population

Patients with Post-Treatment Lyme Disease Syndrome

Number of completers required to accomplish study aims

20

Projected number of subjects who will be enrolled to obtain required number of completers

24

Age range of subject population

New York State Psychiatric Institute INSTITUTIONAL REVIEW BOARD

18-65

Gender, Racial and Ethnic Breakdown Based on prior studies of individuals with Lyme disease, we anticipate the following gender and racial/ethnic group representation:

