Study Objectives	A study is a preliminary investigation regarding the relative benefit of 4 vs 8 weeks of treatment with disulfiram. With this initial study, the investigators will be able to evaluate the side effects, tolerability and initial signs of the effectiveness of disulfiram in reducing symptoms among the 24 patients assessed. The results of this study will guide the investigators regarding whether a larger definitive randomized trial should be conducted, and which treatment schedule is optimal.
Primary endpoint	Week 10 evaluation.
Study Design	A small 14-week randomized placebo-controlled pilot study enrolling 24 patients with persistent symptoms despite prior antibiotic treatment for Lyme disease (known as Post-treatment Lyme Disease Syndrome). Among the 24 disulfiram-treated patients, half will get 8 weeks of disulfiram and the other half will get a shorter duration of disulfiram for 4 weeks followed by 4 weeks of matching placebo. After week 8, patients will be off pills for 2 weeks for the primary week 10 evaluation and then for another 4 weeks for the week 14 follow-up evaluation. This will be a double-blinded study; neither physician nor patient will know which treatment group the patient is assigned to. For details see PSF.
General Study Population	See PSF respective section
Inclusion- Exclusion Criteria	See PSF respective section
Study Assessments	See PSF respective section
Sample size	24 as of 04/02/2019. The study was terminated in 2022 with a sample size of 11.
Randomization	This will be a double-blinded study; neither physician nor patient will know which treatment group the patient is assigned to. Randomization is performed at New York Psychiatric Institute pharmacy when medication is issued to an enrolled participant. Randomization is performed in blocked of 12. The study unblind will occur when the enrollment is completed, and all patients finish their follow-up assessments.
Primary aim#1	To assess the safety and side effect profile of disulfiram among patients with post treatment Lyme symptoms. This will be assessed by SAFTEE (systematically) as well as recording all unanticipated adverse events/serious adverse events.
Primary aim #2	To investigate whether treatment with disulfiram results in a meaningful reduction in fatigue and improvement in the quality of life among patients

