Analysis Analysis Population Missing Data Interim Analyses and Data	The rationale for the Fitbit is that our primary outcome is fatigue. People who are less fatigued may be engaging in more activity, such as doing more steps during the day. Moreover, activity monitoring using a device such as a Fitbit is being increasingly used in research studies as a measure of the change in response to treatment. Analysis will be performed after the study is unblinded. We conduct intent to treat analysis which covers all enrolled patients who received a study drug and who participated in at least one post-baseline assessment. Missing data is treated as missing at random

Primary aim#1 analysis	Tables on all mortality rate, SAE and AE will be generated. To estimate safety, number of adverse events in active and sham treatment groups by the end of 10-week period will be computed and reported.
Primary aim#2 analysis	To investigate whether treatment with disulfiram results in a meaningful reduction in fatigue and improvement in the quality of life, a change in scores between the baseline and week 10 will be computed. We will calculate a number of participants who's change in score reached a minimal clinically significant difference (MCID) for each of the measures. MCID for Fatigue Severity Scale (FSS) and MCID for Quality-of-Life Enjoyment and Satisfaction Questionnaire (Q-LES-Q) is 6.8. A Log Odds ratio for 8-week and 4-week group will be computed along with the 95% confidence interval for this ratio. The 95% confidence interval provides considerably more information than testing a specific null hypothesis: it provides a range of plausible values for differences in these primary outcomes between treatment groups which can be used to inform research in larger studies.

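### An early stopper who plans a new treatment completes the week-10 set early and then has no scheduled side-effect contact, yet the SAP counts adverse events to week 10 without regard to time observed

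*Combined protocol and SAP*

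**What the plan says.** The protocol section on outcome assessment after early discontinuation sets two routes.

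- **Ordinary route.** A participant who stops early is asked back at week 10, or to complete telehealth and local evaluations, and to give self-reports and "telephone follow-up at home at weeks 2, 6, 8, and 14".
- **New-treatment route.** This begins: "Should a patient who drops from treatment early plan to start a new treatment that might impact clinical ratings". The participant completes the full week-10 set early so that it can be analysed, and "that patient will then be discontinued from both the treatment and assessment phase of the study".

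Side effects are collected at scheduled contacts. *Criteria for Early Discontinuation* has participants monitored for "side-effects of the medications (Saftee) during the clinic visits or telehealth visits and weekly phone check-ups". The SAP's Primary aim#1 row adds "recording all unanticipated adverse events/serious adverse events".

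The SAP's Primary aim#1 analysis row states: "number of adverse events in active and sham treatment groups by the end of 10-week period will be computed and reported". I read the two groups there as the 8-week and 4-week arms. The analysis population is "all enrolled patients who received a study drug and who participated in at least one post-baseline assessment". Secondary goal 3 adds: "We will examine the side effect profile and drop-out rate associated with different treatment schedules of disulfiram".

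**The concern.** Once ratings may be driven by another treatment, it makes sense to take the efficacy score early and stop rating. The exit rule, however, ends the assessment phase as a whole and makes no exception for safety contacts. Because SAFTEE is gathered at visits and calls, ending those contacts ends scheduled side-effect capture.

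Safety is a primary aim, and its analysis is a count over a fixed 10-week window. A participant who leaves at week 3 contributes three observed weeks, but the count treats all ten as observed. The SAP has no person-time or censoring rule for this. Its missing-at-random statement does not repair a raw count, in which an unrecorded event is simply absent. The participants concerned have all stopped treatment early. *Overall Progress* reports that treatment drop-out for adverse events exceeded expectation, so some of them may have stopped for safety reasons. If exits differ between arms, the comparison of side effects by schedule is affected as well.

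**Working it through.** The plan states no figure to reproduce, so the check is a side-by-side reading followed by an illustration of scale.

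**1. What is captured up to exit.** The early week-10 set is done first. For all three participation modes, the specimen schedule at week 10 includes blood count and chemistry with liver tests. SAFTEE belongs to visits. Events up to the early visit, including the one that led to stopping, should therefore be recorded.

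**2. What is captured after exit without a scheduled contact.**
- Liver: *Criteria for Early Discontinuation* calls for a repeat test, close monitoring and internist referral, and asks participants to report hepatitis symptoms at once. The section on minimizing risks repeats the monitoring and referral.
- Suicidality: reassessment after one week, and clinical care arranged if the ideation persists.
- Unanticipated or serious events: recorded if they come to notice.

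**3. What is left over.** No scheduled contact remains to find other later events, or to follow the course of a non-liver event such as a neuropathy, between exit and week 10.

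**4. How the SAP treats that time.** The early set is itself a post-baseline assessment, so the participant stays in the analysis population. The count runs to week 10 with no denominator of time observed.

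**5. Scale.** Inputs: 11 enrolled (*Overall Progress*; SAP Sample size), 12 planned per arm (half of 24), and a 10-week window. Exit weeks are assumptions. For one exit at week w among n participants, the unobserved share is (10 − w) / (10 × n).

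| Assumed exit week | Weeks lost | Share of 11 × 10 = 110 | Share of a planned arm, 12 × 10 = 120 |
|---|---|---|---|
| 3 | 10 − 3 = 7 | 7/110 = 6.4% | 7/120 = 5.8% |
| 5 | 10 − 5 = 5 | 5/110 = 4.5% | 5/120 = 4.2% |
| 8 | 10 − 8 = 2 | 2/110 = 1.8% | 2/120 = 1.7% |

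**6. Contacts forgone relative to the ordinary route** (weeks 2, 6, 8, 10 and 14).
- Exit before week 2: five contacts, four of them inside the window.
- Exit at week 3 or 5: weeks 6, 8 and 10 inside the window, plus week 14.
- Exit at week 8: week 10 inside the window, plus week 14.

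**The case against.** **The rule concerns outcome ratings.** It sits in a section on outcome assessment, and its trigger is a treatment that could affect ratings. Safety monitoring is written elsewhere, so the assessment phase might mean efficacy assessment only. That reading is possible. But SAFTEE is itself listed among the assessment instruments, and no text keeps safety contacts going after exit.

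**Other provisions cover safety.** This stands in part. A reader might infer that safety observation ceases altogether at exit. The documents do not support that, because the liver, suicidality and unanticipated-event provisions remain. They are triggered by particular events and do not replace scheduled inquiry. The protocol also offers three months of clinical visits at the end of the study, but does not say whether early leavers qualify.

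**The ordinary route may not collect SAFTEE either.** The protocol justifies those contacts by possible late improvement and does not say that SAFTEE is given at them. The contact counts above therefore show lost opportunities to ask, not a known number of lost SAFTEE forms.

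**Later events are confounded by the new treatment.** True, and in a small pilot it is a defensible reason to stop rating efficacy. For safety it argues for dating and flagging such events, not for leaving them uncollected.

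**The analysis is descriptive and drop-out is reported by schedule.** This keeps the point small. A drop-out rate still does not show how long each participant was observed.

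**Conclusion.** The point holds as a minor one, with moderate confidence. The exit rule, combined with a fixed-window count and no allowance for time observed, makes unobserved weeks look event-free under primary aim 1. The gap is limited to scheduled capture of other later events, and of the course of non-liver events, from the early exit to week 10.

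Its size in this study is unknown. The shares of 1.8% to 6.4% per exit rest wholly on assumed exit weeks, and nothing shows that anyone left by this route. Because 10 of 11 are reported as having completed, a reader might infer that at most one participant could be affected. That does not follow: completion is not defined, and someone who did the week-10 set early could be counted as a completer.

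A reader might also infer that the week-10 responder result is lost for these participants, or that the adverse-event counts are shown to be biased. Neither is supported. The early set supplies an efficacy score, and the documents give no exit dates or event data from which to judge bias.

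**What to change.** **SAP, usable now.** In the Primary aim#1 analysis, report weeks observed per participant and person-weeks per arm beside the adverse-event counts. Flag early exits, and flag events that began after a new treatment where start dates are known. This costs one table column and the flags.

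**Protocol, for the follow-on trial.** Enrollment has ended, so this part cannot help the present study. In the early-discontinuation section, let the new-treatment exit end only the efficacy ratings. Record the new treatment and its start date. With the participant's agreement, continue brief side-effect telephone contacts through week 10 and at week 14.

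On the ordinary route's schedule this is at most five contacts, when exit precedes week 2. If they are run like the protocol's existing 10-20 minute calls, that is 5 × 10 = 50 to 5 × 20 = 100 minutes per affected participant, and less for later exits. Week 10 is an evaluation on the ordinary route; a call would replace it here. Some participants may decline, and the weeks-observed column would show that.
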